| MedDRA | Medical Dictionary for Regulatory Activities |
| MTD | Maximum Tolerated Dose |
| NIH | National Institutes of Health |
| NIDDK | National Institute of Diabetes and Digestive and Kidney Diseases |
| PI | Principal Investigator |
| rtCGM | Real-time continuous glucose monitoring |
| SAE | Serious Adverse Event |

STATEMENT OF COMPLIANCE

I confirm that I have read this protocol, and I will conduct the study as outlined herein and according to the ethical principles stated in the latest version of the Declaration of Helsinki, the U.S. code of federal regulations (CFR) applicable to clinical studies (45 CFR Part 46, 21 CFR Part 50, 21 CFR Part 56, 21 CFR Part 312 and/or 21 CFR Part 812), and the applicable ICH guidelines for Good Clinical Practice (GCP).

I will promptly submit the protocol to the IRB for review and approval. Once the protocol has been approved by the IRB, I understand that any modifications made during the course of the study must first be approved by the IRB prior to implementation except when such modification is made to remove an immediate hazard to the subject.

I will provide copies of the protocol and all pertinent information to all individuals responsible to me who assist in the conduct of this study. I will discuss this material with them to ensure that they are fully informed regarding the study treatment, the conduct of the study, and the obligations of confidentiality.

Note: This document is signed electronically through submission and approval by the Principal Investigator in the University of Utah IRB Electronic Research Integrity and Compliance Administration (ERICA) system.

STUDY SUMMARY

| Title | The Use of Amitriptyline for Improving Hypoglycemia Recognition and Course | | | |
|---------------------------|--|--|--|--|
| Short Title | Amitriptyline as an anti-hypoglycemic agent | | | |
| Protocol Number | IRB # 00110853 | | | |
| IND | Pending – applying for IND exemption | | | |
| Phase | Pilot, clinical phase II | | | |
| Design | Double blind, randomized, placebo control, cross- over design | | | |
| Study Duration | 38 weeks | | | |
| Study Center(s) | University of Utah Hospital and Clinics | | | |
| Objectives | To evaluate whether amitriptyline improves the hypoglycemia course and the ability to recognize hypoglycemia in type 1 diabetes patients who are using real-time continuous glucose monitoring devices | | | |
| Number of Subjects | Approximately 80 participants for Run-in Period, with a goal of randomizing 24 patients for drug intervention phase | | | |
| Main Eligibility Criteria | Inclusion Criteria Subjects with T1DM for one years or more Age between 21 to 60 years old HbA1c less or equal to 9% with the last measurement in the last three months Ongoing use of real-time CGM for at least 3 months Exclusion Criteria Ongoing or recent history of major depressive disorder, or other ongoing major psychiatric disorders History of anti-depressant use within the last three months History of advanced cardiac, liver, kidney and neurological disease Active malignant or HIV diseases Advanced diabetic retinopathy, neuropathy or nephropathy Female in pregnancy or not able to practice effective contraception during the study period Contraindication to amitriptyline use | | | |

| | < 70% of CGM readings available over the last 2-week period Time spent in hypoglycemia (i.e., < 70 mg/dL) for < 5% over a 2-week period on based on CGM reading |
|-------------------------------------|---|
| Study Product, Dose, Route, Regimen | Amitriptyline 25 mg and 50 mg oral daily at bedtime |
| Duration of Administration | Up to 12 weeks |
| Reference Therapy | Placebo |
| Statistical Methodology | The Wilcoxon rank sums test as adapted to determine study outcomes. Hodges-Lehman estimates and associated exact 95% confidence intervals will provide estimates of the size of the treatment effect. |

Protocol Title: The Use of Amitriptyline for Improving Hypoglycemia Course and Recognition Version Date: March 24, 2018 Principal Investigator: [name]

STUDY SCHEMA

Protocol Title: The Use of Amitriptyline for Improving Hypoglycemia Course and Recognition Version Date: March 24, 2018 Principal Investigator: [name]

1. OBJECTIVES

The overall goal of the current study is to evaluate whether amitriptyline improves the hypoglycemia course and the ability to recognize hypoglycemia in type 1 diabetes patients who are using real-time continuous glucose monitoring (rtCGM) devices.

1.1 Primary Objectives and Endpoints

- The area-under-curve (AUC) of glucose <70 and 54 mg/dL on continuous glucose monitoring (CGM).
- The ratio of recognized-to-total hypoglycemic episodes.

1.2 Secondary Objectives and Endpoints

- Count of severe hypoglycemic episodes.
- Hypoglycemic course, including episode count, total time, average time/episode, and percentage of glucose < 70, 54 and 40 mg/dL; AUC of glucose < 40 mg/dL; average nadir glucose.
- Nocturnal hypoglycemic course, including episode count, total time, average time/episode, percentage and AUC of glucose < 70, 54 and 40 mg/dL; average nadir glucose.
- Hypoglycemia awareness score (Gold [1], Clarke [2] and Pedersen-Bjergaard [3]).
- Other glucose regulation: Average glucose, glycemic variability, time in hyperglycemia with level above 180, 250 and 300 mg/dL, percentage of time in normal glucose, HbA1c.
- Hypoglycemia Fear Survey score [4].

2 BACKGROUND

Poorly controlled type 1 diabetes mellitus (T1DM) can lead to serious and devastating complications, including microvascular (retinopathy, neuropathy and nephropathy) and cardiovascular disease. Both diabetic microvascular and cardiovascular complications can be reduced by intensive insulin therapy and strict blood glucose control aiming for hemoglobin A1C (HbA1c) less or equal to 7%. [5, 6] However, a tighter glycemic control correlates with a higher incidence of hypoglycemia. [7] Recurrent episodes of hypoglycemia induce an attenuation or loss of catecholamine counter-regulatory responses (a condition termed hypoglycemia-associated autonomic failure) and the ability to recognize hypoglycemic episodes (impaired awareness of hypoglycemia). [8, 9] Hypoglycemia-associated with a 25 and six-fold increased risk of severe hypoglycemia, respectively. [9-11] Severe hypoglycemia leads to seizures, emergency room visits/hospitalization, fear of hypoglycemia, compromised quality of life and potentially death. [12] Thus, hypoglycemia-

associated autonomic failure and impaired awareness of hypoglycemia are major barriers to optimal glycemic control. [8]

Real-time continuous glucose monitoring (rtCGM) is a technique which measures interstitial glucose levels every five minutes to estimate coincidental blood glucose levels. [13] A rtCGM will alert patients of hyper/hypoglycemic events at set glucose thresholds and when the blood glucose levels are rapidly rising/declining. While rtCGM has demonstrated to significantly decrease the daily time spent in hypoglycemia, patients wearing rtCGM still spend approximately 3-7% of time in hypoglycemia in average, equivalent to 43-101 minutes in a day.[14-16] While the prevalence of T1DM using CGM is rapidly increasing, there has been no adjuvant therapy demonstrating its ability to further decrease the hypoglycemic burden for this patient population.

In the current study, we propose to test amitriptyline, a tricyclic antidepressant, as an adjuvant treatment of rtCGM to further improve hypoglycemia course and T1DM patients' ability to recognize hypoglycemic episode. Our lab has constructed a 2-Deoxy-D-glucose (2DG)-mediated impaired awareness model in rats, in order to identify therapies for rapid translational testing and clinical use. 2DG blocks normal glucose metabolism and causes cellular glucose deprivation. Repeated 2DG infusions thus assimilate repetitive "cellular hypoglycemia". [17] Based on this concept, our lab has developed a rodent model of repetitive 2DG infusion-mediated impaired hypoglycemia awareness. We use the amount of food intake in response to subsequent insulin-induced hypoglycemia as an objective measurement of impaired awareness in this model, as food intake is an important behavioral defensive mechanism and can reflect hunger (a hypoglycemic symptom).

In our model, rats decreased food intake during a subsequent insulin-mediated hypoglycemic episode after repetitive 2DG infusion (figure 1), evident for the development of impaired hypoglycemia awareness. After testing 50+ drugs, we observed that amitriptyline both prevented and restored the attenuated food intake response (figure 2). [18] These findings suggest that amitriptyline has a potential role in clinically improving hypoglycemic course. In addition, amitriptyline is a common and safe therapy for diabetic neuropathy. [19-21] We therefore propose that amitriptyline is a strong testing candidate for mitigating hypoglycemia burden in T1DM patients.

3 DRUG INFORMATION

Amitriptyline (investigational drug) has been approved by the FDA for indications unrelated to the current study. [22] In the current study, we will use amitriptyline as our investigational drug. A summary of the FDA label for amitriptyline has been provided in the following:

DESCRIPTION

Amitriptyline HCl, a dibenzocycloheptadiene derivative, is a white, or practically white, odorless, crystalline compound which is freely soluble in water and alcohol.

It is designated chemically as 10,11-Dihydro-N,N-dimethyl- 5*H*-dibenzo[a,d] cycloheptene- Δ 5, γ -propylamine hydrochloride. It has the following structural formula:

C₂₀H₂₃N • HCl M.W. 313.87

Each tablet for oral administration contains 10, 25, 50, 75, 100, or 150 mg amitriptyline hydrochloride.

CLINICAL PHARMACOLOGY

Amitriptyline HCl is an antidepressant with sedative effects. Its mechanism of action in man is not known. It is not a monoamine oxidase inhibitor and it does not act primarily by stimulation of the central nervous system.

Amitriptyline inhibits the membrane pump mechanism responsible for uptake of norepinephrine and serotonin in adrenergic and serotonergic neurons. Pharmacologically, this action may potentiate or prolong neuronal activity since reuptake of these biogenic amines is important physiologically in terminating transmitting activity. This interference with reuptake of norepinephrine and/or serotonin is believed by some to underlie the antidepressant activity of amitriptyline.

DOSAGE AND ADMINISTRATION

Oral Dosage

Dosage should be initiated at a low level and increased gradually, noting carefully the clinical response and any evidence of intolerance.

Initial Dosage for Adults

For outpatients, 75 mg of amitriptyline HCl a day in divided doses is usually satisfactory. If necessary, this may be increased to a total of 150 mg per day. Increases are made preferably

in the late afternoon and/or bedtime doses. A sedative effect may be apparent before the antidepressant effect is noted, but an adequate therapeutic effect may take as long as 30 days to develop.

An alternate method of initiating therapy in outpatients is to begin with 50 to 100 mg amitriptyline HCl at bedtime. This may be increased by 25 or 50 mg as necessary in the bedtime dose to a total of 150 mg per day.

Hospitalized patients may require 100 mg a day initially. This can be increased gradually to 200 mg a day if necessary. A small number of hospitalized patients may need as much as 300 mg a day.

500 mg a day.

Maintenance

The usual maintenance dosage of amitriptyline HCl is 50 to 100 mg per day. In some patients, 40 mg per day is sufficient. For maintenance therapy, the total daily dosage may be given in a single dose, preferably at bedtime. When satisfactory improvement has been reached, dosage should be reduced to the lowest amount that will maintain relief of symptoms. It is appropriate to continue maintenance therapy 3 months or longer to lessen

the possibility of relapse.

Plasma Levels

Because of the wide variation in the absorption and distribution of tricyclic antidepressants in body fluids, it is difficult to directly correlate plasma levels and therapeutic effect. However, determination of plasma levels may be useful in identifying patients who appear to have toxic effects and may have excessively high levels, or those in whom lack of absorption or noncompliance is suspected. Because of increased intestinal transit time and decreased hepatic metabolism in elderly patients, plasma levels are generally higher for a given oral dose of amitriptyline hydrochloride than in younger patients. Elderly patients should be monitored carefully and quantitative serum levels obtained as clinically appropriate. Adjustments in dosage should be made according to the patient's clinical response and not on the basis of plasma levels. For this study, as we are using low amitriptyline dose, we will not conduct plasma level monitoring.

METABOLISM

Studies in man following oral administration of 14C-labeled drug indicated that amitriptyline is rapidly absorbed and metabolized. Radioactivity of the plasma was practically negligible, although significant amounts of radioactivity appeared in the urine by 4 to 6 hours and one-half to one-third of the drug was excreted within 24 hours.

Amitriptyline is metabolized by N-demethylation and bridge hydroxylation in man, rabbit, and rat. Virtually the entire dose is excreted as glucuronide or sulfate conjugate of metabolites, with little unchanged drug appearing in the urine. Other metabolic pathways

may be involved.

INDICATION, CLINICAL USE, ADVERSE EVENT, CONTRAINDICATIONS AND PREGNANCY IMPLICATION

Amitriptyline is indicated for depression/major depressive disorder. Prior studies also supported its effectiveness in treating diabetic neuropathy [23], chronic pain management [24], fibromyalgia [25], insomnia [26], interstitial cystitis [27], irritable bowel syndrome [28], postherpetic neuralgia [29], post-traumatic stress disorder [30] and sialorrhea (excessive production of saliva) [31], and preventing migraine [32].

The following adverse events were observed and have been reported in patients using amitriptyline:

- Cardiovascular: Atrioventricular conduction disturbance, cardiac arrhythmia, cardiomyopathy (rare), cerebrovascular accident, ECG changes (nonspecific), edema, facial edema, heart block, hypertension, myocardial infarction, orthostatic hypotension, palpitations, syncope, tachycardia
- Central nervous system: Anxiety, ataxia, cognitive dysfunction, coma, confusion, delusions, disorientation, dizziness, drowsiness, drug withdrawal (nausea, headache, malaise, irritability, restlessness, dream and sleep disturbance, mania [rare], and hypomania [rare]), dysarthria, EEG pattern changes, excitement, extrapyramidal reaction (including abnormal involuntary movements and tardive dyskinesia), fatigue, hallucination, headache, hyperpyrexia, insomnia, lack of concentration, nightmares, numbness, paresthesia, peripheral neuropathy, restlessness, sedation, seizure, tingling of extremities
- Dermatologic: Allergic skin rash, alopecia, diaphoresis, skin photosensitivity, urticarial
- Endocrine & metabolic: Altered serum glucose, decreased libido, galactorrhea, gynecomastia, increased libido, SIADH, weight gain, weight loss
- Gastrointestinal: Ageusia, anorexia, constipation, diarrhea, melanoglossia, nausea, paralytic ileus, parotid gland enlargement, stomatitis, unpleasant taste, vomiting, xerostomia
- Genitourinary: Breast hypertrophy, impotence, testicular swelling, urinary frequency, urinary retention, urinary tract dilation
- Hematologic & oncologic: Bone marrow depression (including agranulocytosis, leukopenia, and thrombocytopenia), eosinophilia, purpura
- Hepatic: Hepatic failure, hepatitis (rare; including altered liver function and jaundice)
- Hypersensitivity: Tongue edema
- Neuromuscular & skeletal: Lupus-like syndrome, tremor, weakness
- Ophthalmic: Accommodation disturbance, blurred vision, increased intraocular pressure, mydriasis
- Otic: Tinnitus
- Postmarketing and/or case reports: Angle-closure glaucoma, neuroleptic malignant syndrome (rare), serotonin syndrome (rare)

The contraindications of amitriptyline are hypersensitivity to amitriptyline or any component of the formulation; coadministration with or within 14 days of MAOIs; coadministration with cisapride; acute recovery phase following myocardial infarction.

Amitriptyline can be used as an antidepressant. Antidepressants increase the risk of suicidal thinking and behavior in children, adolescents, and young adults (18 to 24 years of age) with major depressive disorder and other psychiatric disorders. For the current study, patients with ongoing and recent history of depression or other major psychiatric disorders will be excluded from recruitment. Furthermore, short-term studies did not show an increased risk in patients >24 years of age and showed a decreased risk in patients ≥ 65 years.

Amitriptyline is Pregnancy Category C. Adverse events have been observed in some animal reproduction studies. Amitriptyline crosses the human placenta; CNS effects, limb deformities, and developmental delay have been noted in case reports (causal relationship not established). Tricyclic antidepressants may be associated with irritability, jitteriness and convulsions (rare) in the neonate. Crying, constipation, problems with urinating, and nausea may also occur in neonate exposed during pregnancy. For the current study, pregnancy will be ruled out before initial recruitment and before study drug intervention. Consultation for contraception will also be provided.

4 STUDY DESIGN

4.1 Description

The current investigation is a pilot phase II clinical trial with placebo control, randomization and double-blinding design.

After the initial recruitment (Visit 1), the study participants will enter a two-week "Runin Period", during which the participants will be asked to continue their CGM use and record their symptom(s) on Hypoglycemic Event Reports for all their hypoglycemic events. For the participants who meet the criteria to be initiated on study drug (see recruitment criteria), they will then be randomized to be initiated either on daily amitriptyline or a matching placebo (Visit 2). All participants will undergo a two-week drug "Titration Period", and at the end of this period (i.e., the end of Week 4), the amitriptyline dose will be titrated up with a matching placebo and continued until Visit 4. During this "Intervention Period", the patient will receive telephone follow-ups at Week 5 and Week 7, and undergo a return visit (Visit 3). After Visit 3, the participants will again start to record their hypoglycemic symptoms, and then return to Visit 4 at the end of the Intervention Period. The participants will then undergo a two-week study drug "Tapering Period" to complete the study drug intervention. At week 27 and 39 of the study, the participants will be assessed with follow-up questionnaires.

4.2 Number of Subjects

Up to 80 participants are expected to be enrolled into the study for the Run-in Period assessment. For the study drug testing phase, 24 participants will be randomized and equally divided into two arms (i.e., 12 participants in the amitriptyline arm and 12 participants in the matching placebo arm).

4.3 Number of Study Centers

This study will be a single-center study conducted at the University of Utah.

4.4 Study Duration

The pilot study is expected to last for two years, and will help provide the estimated time for the final study. The duration of each patient's participation in the study will be 39 weeks, with 15 weeks of active assessment/intervention and 24 weeks of distant follow-up.

5 ELIGIBILITY CRITERIA

This checklist is used to determine subject eligibility; it should be completed for each subject, including review and signature by the enrolling investigator and filed in the subject research chart.

Subject ID: _____

Subject Initials:

5.1 Inclusion Criteria

Yes/No (a response of 'No' indicates the subject is ineligible)

- 1. _____ Subjects with T1DM for \geq five year or more
- 2. _____ Age between 21 to 60 years old
- 3. _____ HbA1c less or equal to 9% with the last measurement in the last three months
- 4. Use of rtCGM providing continuous glucose data points for at least 3 months with $\ge 80\%$ of CGM readings over the last 2-week period
- 5. _____ Able to provide informed consent and willing to sign an approved consent form that conforms to federal and institutional guidelines.

5.2 Exclusion Criteria

Yes/No (a response of "Yes" indicates the subject is ineligible)

- 1. _____ Ongoing or recent history of major depressive disorder, or other ongoing major psychiatric disorders
- 2. _____ History of anti-depressant use within the last three months
- 3. _____ Insulin pump linked to a CGM with programmed automatic insulin adjustment/suspension

- 4. _____ History of advanced cardiac, liver, kidney and neurological disease
- 5. _____ Active malignant
- 6. _____ Uncontrolled HIV diseases
- 7. _____ Advanced diabetic retinopathy, neuropathy or nephropathy
- 8. _____ Frequent acetaminophen use which can disrupt CGM accuracy
- 9. _____ Pregnancy or female of child-bearing potential unable to practice effective contraception during the study period
- 10. _____ Breastfeeding female or female with prospective plan to initiate breastfeeding
- 11. _____ Ongoing history of alcohol abuse
- 12. _____Contraindication to amitriptyline use, including hypersensitivity to amitriptyline or any component of the formulation, coadministration with or within 14 days of MAOIs and coadministration with cisapride
- 13. _____ Inability to understand or cooperate with study procedure, including taking study drugs and record hypoglycemic symptoms

The participants meeting the above criteria will enter "Run-in Period". At the Visit 2, the following additional exclusion criteria will be applied before study drug randomization:

- 14. _____ < 80% of CGM readings available over the last 2-week period
- 15. _____ Time spent in hypoglycemia (i.e., < 70 mg/dL) for < 5% over a 2week period on based on CGM reading.

I verify that this subject meets all eligibility criteria for enrollment onto this study

Investigator Signature

Date

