9.10.1 Primary Objective Assessment

The primary objective assessment will be done through the determining areaunder-curve for CGM glucose level < 70/54 mg/dL and the total and recognized hypoglycemic episodes based on CGM data and hypoglycemic event reports, respectively.

A single CGM hypoglycemic episode will be defined by any CGM readings < 70 mg/dL lasting equal to or more than 20 minutes on the CGM data.

A participant will complete a hypoglycemic event report for all hypoglycemic events during the surveillance periods. A hypoglycemic event report will include information about whether the participants perceive symptom(s) for hypoglycemic episodes recorded based on CGM.

At each visits, CGM data will be downloaded into a secure system and exported into an Excel format, and the hypoglycemic event reports will be prepared for analysis.

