9.10.2 Secondary Objective Assessment

In brief, the count of severe hypoglycemic episodes will be generated by participant surveillance at each Visit/telephone call. The hypoglycemic/nocturnal hypoglycemic courses, and other glucose regulation will be assessed with CGM data download and venous blood HbA1c assessment. A nocturnal hypoglycemia will be defined for all hypoglycemic episodes occur during 00:00-06:00 on CGM clock. Hypoglycemia awareness status and fear of hypoglycemia status will be assessed through hypoglycemia awareness questionnaires (Gold, Clark and Pedersen-Bjergaard) and Hypoglycemia Fear Survey Questionnaire. CGM data will be collected at Visit 1-4, and the questionnaires will be completed by study subjects at the first, second and the last Visit, and with the follow-up phone calls.

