10 STATISTICAL CONSIDERATIONS

The statistical analyses of the pilot study will evaluate feasibility and address questions concerning trial conduct and outcomes, as well as power analysis for sample size which must be resolved in order to develop a rigorous design for the full scale trial of the final study. These analyses will be primarily descriptive.

The statistical analyses to evaluate the effects of the intervention on the primary and secondary outcomes will be conducted in both the pilot and final studies. For the pilot study, we will apply the exact Wilcoxon rank sums test as adapted to compare the primary outcome defined by the ratio of recognized-to-total (i.e. CGM) hypoglycemic events between the amitriptyline and placebo treatments under the assumption of no-carry over effects. Hodges-Lehman estimates and associated exact 95% confidence intervals will provide estimates of the size of the treatment effect. Other outcomes will be analyzed using either a similar nonparametric approach or mixed effect models parameterized to estimate the effects of treatment and period.

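### The CGM outcomes have no planned baseline covariate, although two pre-drug fortnights are collected, and selection at Visit 2 makes any change from run-in unsafe to read as a drug effect

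*Combined protocol and SAP*

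**What the plan says.** Participants complete a two-week run-in, "during which the participants will be asked to continue their CGM use and record their symptom(s) on Hypoglycemic Event Reports" (section 4.1). Section 5.2 then states: "At the Visit 2, the following additional exclusion criteria will be applied before study drug randomization". Criterion 15 is the hypoglycemia threshold, which removes anyone with "Time spent in hypoglycemia (i.e., < 70 mg/dL) for < 5% over a 2week period on based on CGM reading". Section 4.2 expects up to 80 people in the run-in and 24 randomised, 12 per arm.

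Two pre-drug stretches of CGM exist. Inclusion criterion 4 (section 5.1) requires at least 80% "of CGM readings over the last 2-week period" at entry and sets no hypoglycemia threshold for that fortnight. The run-in follows. Section 9.10.1 says "At each visits, CGM data will be downloaded into a secure system and exported into an Excel format", and section 9.10.2 says "CGM data will be collected at Visit 1-4".

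The primary endpoints (section 1.1) are the AUC of glucose below 70 and 54 mg/dL and the recognised-to-total ratio. Section 10 gives the ratio an exact rank-sum test between treatments. It leaves other outcomes to a similar nonparametric approach or to "mixed effect models parameterized to estimate the effects of treatment and period". No baseline covariate or change score is named for any outcome, no period is named as the CGM baseline, and regression to the mean is not mentioned.

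**The concern.** A fortnight's time below 70 mg/dL is a noisy measure of a person's usual burden. Keeping only people above a cut-off on that measure retains some whose fortnight was worse than usual for them. Their next values fall back on average, with or without drug. Truncating the run-in also weakens it as a predictor of the outcome.

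Two things are at stake. First, anyone who reports change from run-in within an arm, or plans the next trial from run-in values, will see a fall that is not a drug effect or a burden that is too high. Second, with 12 per arm, leaving pre-drug CGM out of the between-arm analysis gives up precision on the CGM endpoints that existing data could supply.

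**Working it through.** **Inputs from the documents.** Threshold 5%. Background (section 2): time in hypoglycemia averages 3-7%, given as 43-101 minutes a day. This reproduces: 0.03 × 1440 = 43.2 and 0.07 × 1440 = 100.8. Randomised: 24, 12 per arm. The plan states no power calculation, SD or between-fortnight correlation, so there is no further figure to reproduce.

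**Assumptions.** Percent time below 70 mg/dL is lognormal with mean 5% (mid-point of 3-7%) and CV 0.8. The log-scale correlation r between fortnights is 0.5-0.8.

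**Step 1: untreated fall.**
- σ = √ln(1 + 0.8²) = 0.703.
- μ = ln 5 − σ²/2 = 1.362.
- Standardised cut-off c = (ln 5 − μ)/σ = 0.352.
- Share passing = 1 − Φ(c) = 0.363.
- Mean run-in value of those selected = 5 × Φ(σ − c)/0.363 = 5 × 0.638/0.363 = 8.8%.
- Mean later value without treatment = 5 × Φ(rσ − c)/0.363. At r = 0.5 this is 5 × 0.500/0.363 = 6.9%. At r = 0.8 it is 5 × 0.584/0.363 = 8.0%.
- Fall: 22% at r = 0.5 and 8% at r = 0.8. With population means of 3% and 7%, the range widens to 5-34%.

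The direction needs only r below 1; the size rests on the assumptions. With equal correlations, the pre-Visit 1 fortnight of the selected group has the same expected value as the later one, so it shows no such fall.

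**Step 2: does this harm the tests?** In 4,000 simulated trials of 12 per arm with no drug effect (30% pass rate, r = 0.7, log-SD 0.8), the between-arm rank-sum test rejected in 4.2% of trials on later values and 4.4% on change from run-in. The randomised comparison keeps its size. A within-arm signed-rank test on change from run-in was significant in 29% of placebo arms.

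**Step 3: value of a baseline covariate.** Let A be the pre-Visit 1 fortnight, B the run-in and Y the later fortnight, on the log scale. Selection on B shrinks its variance by k = 1 − λ(λ − c), where λ = φ(c)/(1 − Φ(c)) = 1.034, so k = 0.294. After selection each covariance is T(i,j) = ρ(i,j) − (1 − k)ρ(i,B)ρ(j,B), in units of the unselected variance. For the average of A and B:

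R² = [T(A,Y) + T(B,Y)]² / {[T(A,A) + T(B,B) + 2T(A,B)] × T(Y,Y)}.

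At r = 0.65 throughout: T(A,Y) = 0.352, T(B,Y) = T(A,B) = 0.191, T(A,A) = T(Y,Y) = 0.702, T(B,B) = 0.294. So R² = 0.543²/(1.377 × 0.702) = 0.305. The run-in alone gives 0.191²/(0.294 × 0.702) = 0.177.

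With 24 participants in two arms, one covariate multiplies the expected variance by 1 + 1/(24 − 4) = 1.05. The variance relative to no adjustment is therefore 1.05 × (1 − R²). The last four rows let correlation decay with time.

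| Correlations A-B / B-Y / A-Y | R² run-in | R² average | Variance ratio, run-in | Variance ratio, average |
|---|---|---|---|---|
| 0.50 / 0.50 / 0.50 | 0.089 | 0.190 | 0.96 | 0.85 |
| 0.65 / 0.65 / 0.65 | 0.177 | 0.305 | 0.86 | 0.73 |
| 0.80 / 0.80 / 0.80 | 0.343 | 0.473 | 0.69 | 0.55 |
| 0.75 / 0.55 / 0.50 | 0.113 | 0.130 | 0.93 | 0.91 |
| 0.80 / 0.60 / 0.50 | 0.142 | 0.116 | 0.90 | 0.93 |
| 0.65 / 0.65 / 0.42 | 0.177 | 0.103 | 0.86 | 0.94 |
| 0.50 / 0.50 / 0.25 | 0.089 | 0.042 | 0.96 | 1.01 |

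The average lowers variance by 6-45% in every row but the last, where it gains nothing. It beats the run-in alone under equal correlation or mild decay, and does slightly worse under steep decay.

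**Step 4: illustrative power.** For a halving of time low in the Step 2 setting, ANCOVA has power 0.79 with the run-in as covariate and 0.83 with both fortnights. The unadjusted rank-sum test has 0.68, though part of that gap is the change of test.

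**The case against.** The strongest reply is that nothing here is an error. The plan does not call the run-in the CGM baseline, plans no within-arm test, and compares arms by randomisation. Its description of the analyses as mainly descriptive is attached to feasibility and trial conduct. Nothing says that run-in values will feed the next trial's planning. Visit 1 CGM is already listed as collected for the hypoglycemia outcomes, and nothing keeps it out of the mixed models. All of this stands. The point is an omission in the specification and a caution about interpretation.

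The precision gain can also be challenged. It rests on correlations that the documents do not give, and the advantage over the run-in alone shrinks or disappears if correlation decays. A second separate covariate would cost about 5% more variance ((1 + 2/19)/1.05 = 1.053). That stands too, and is why a single averaged covariate is preferable. The calculation concerns percent time below 70 mg/dL, a secondary outcome. The AUCs measure the same burden, but their gain may differ in size.

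A reader might infer two stronger points that the documents do not support:
- The period effect in section 10 could be taken as a before-after contrast inflated by selection. That wording sits beside an assumption of no carry-over, and the Study Summary calls the design cross-over, so it reads as leftover crossover language.
- Criterion 15 refers to a fortnight without saying which, so a worse one might seem selectable from months of CGM. It is applied at Visit 2, directly after criterion 14, which refers to the latest two weeks. It points to the run-in.

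**Conclusion.** The point holds as a low-cost improvement. Selection at Visit 2 implies a later fall in both arms without treatment, about 8-22% under the assumed mean of 5%, CV of 0.8 and correlation of 0.5-0.8. It would be wrong to conclude that the treatment comparison is biased: both arms are selected alike before randomisation, and the simulated between-arm tests kept their size.

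What the plan lacks is a stated covariate for the CGM outcomes, including both primary AUCs. Relative to no adjustment, one averaged pre-drug covariate lowers variance by about 6-45% after its degree-of-freedom cost, with no gain in the least favourable case examined. Its gain over adjusting for the run-in alone is modest and may be nil or slightly negative.

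The recognised-to-total ratio, the only outcome with a named test, is outside the fix. Event reports start after Visit 1 and resume late in treatment ("After Visit 3, the participants will again start to record their hypoglycemic symptoms"), so the pre-Visit 1 fortnight has none.

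**What to change.** In section 10, for each CGM outcome:

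- Make the between-arm analysis a linear model or rank-based ANCOVA with treatment and one baseline covariate: the average of the pre-Visit 1 and run-in fortnights. Fix the scale in advance (log or rank), with a rule for zero values, which are likely for AUC below 54 mg/dL.
- State that change from run-in within an arm will not be interpreted as a treatment effect, because participants were selected on that fortnight.
- Take burden and variance for planning the next trial from the placebo arm's on-treatment data, not from the run-in.

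Leave the analysis of the recognised-to-total ratio as it is on this point. The cost is one degree of freedom, a few sentences, and one extra summary per participant from the Visit 1 download. No new visit, participant or measurement is needed.
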